1.4 Sample Size Justification

The study was targeted to enroll 270 participants with confirmed severe or critical COVID-19 disease in a 2:1 manner, with approximately 180 participants in the Sirukumab treatment arm and approximately 90 participants in the control arm. However, based on the rapidly evolving space of COVID-19 therapeutics focusing on the highly impacted population of critical patients together with the results from the interim analysis, the study population is being limited with protocol amendment 5 to a subset of the currently eligible population, ie, those with confirmed critical COVID-19 disease.

At the time of release of protocol amendment 5, approximately 100 participants with confirmed severe COVID-19 had been enrolled.

The study aims to enroll approximately 111 participants with confirmed critical COVID-19 disease overall in the study, with approximately 74 participants in the Sirukumab treatment arm and approximately 37 participants in the control arm.

The primary endpoint in this study is the time to sustained improvement of at least 2 categories relative to

Baseline on the 6-point ordinal clinical recovery scale, with participants who die prior to Day 28 treated as right censored at Day 28. For the sample size calculation on the primary endpoint, the following assumptions are used for survivors and participants who die prior to Day 28:

- For survivors in the control arm, it is assumed that the log transformed time to sustained improvement (days) follows a normal distribution with mean of log 28 and a standard deviation 0.9. Sirukumab is assumed to reduce the median time to sustained clinical improvement from 28 days to 16.8 days (40% reduction) in the surviving participants and is assumed to have the same standard deviation of 0.9.
- For the mortality rate in the control arm, 40% by Day 28 is assumed. Sirukumab is assumed to reduce the mortality with an absolute difference of 20%: from a mortality rate of 40% in the control arm to 20% (50% relative reduction).

Under these assumptions, at least 111 participants with confirmed critical COVID-19 disease are required to have at least 80% power to demonstrate a difference with the log-rank test, at a significance level of 5% two-sided.

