| Time to Mechanical Ventilation (up to Day 28) (days) among participants not on mechanical ventilation at Baseline [Time-to event] | Similar as for the primary endpoint, but with a score of 5 on the CRS (instead of an improvement of 2 categories). Participants who did not evolve to score 5 and who die will be censored at the day of death. This endpoint will be evaluated in the subgroup of participants for which the CRS is less than 5 at Baseline. |
| Time from study intervention to ICU discharge (up to Day 28) among the participants on ICU at baseline (days) [Time-to event] | Subjects who die at or before day 28 will be censored on day 28. Subjects alive on day 28: Only ICU periods with a starting day \leq day 28 are taken into account. Missing end dates of ICU periods are imputed with the cut-off date (for ongoing subjects) or the date of study discontinuation/completion - If last ICU stay end date $<$ minimum(date visit day 28, study discontinuation, study completion), -> the subject has an event on the last day in the ICU + 1 day. - If last ICU stay end date \geq minimum (date visit day 28, study discontinuation, study completion), -> the subject will be censored on minimum(day 28, day study discontinuation, day study completion). |
| Total length of hospitalization among the surviving participants (up to Day 28) (days) [Duration] | The total number of days a subject stayed in the hospital during the period from study drug intake until day 28, calculated as sum of the individual hospitalization periods, including re-hospitalizations. This endpoint will be evaluated in the subgroup of participants who were still alive at day 28 The total length of hospitalization will be missing for participants who discontinue the trial for other reason than death before day 28. |
| Number of ventilation free days in participants on IMV/ECMO at baseline (up to Day 28) (days) [Duration] | Calculated as: Date day 28 – maximum date of day with score ≥ 5 Participants who die will be considered as being on IMV/ECMO until day 28. |

| | |
|---|--|
| Improvement at day 28 on the CRS with at least 1 category at day 28 (or at discharge/discontinuation) [Incidence] | CRS improved with at least 1 category at day 28 (or at discharge/discontinuation) when compared to baseline (Yes/No) |

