5.4.2 Analysis Methods

The secondary endpoint evaluation will be conducted on the primary and on the ITT population.

Time-to event parameters

The time-to-event parameters will be evaluated based on the log-rank test, stratified for the stratification factors (age [<65 and ≥ 65 years] and use of IMV [yes/no]). The tests will be performed 1-sided at a 5% significance level. The actual values of the stratification factors will be used, not as randomized.

Cumulative proportion of patients with an event, by treatment, will be provided using the complement of the Kaplan Meier curve. The analyses will be completed with the median time to event (if reached) and the proportion of participants who with an event on day 7, 14, 21 and 28; all per Kaplan Meier method. The complementary log-log transform method is used to calculate the 90% confidence intervals.

Duration parameters

Descriptive statistics of the duration parameters will be shown for all participants that were still alive at day 28.

Total length of hospitalization and number of ventilation free days will be analyzed in the subgroup of participants that were still alive at day 28 by using the Hodges-Lehman approach. Corresponding 90% CIs will be presented as well.

Incidence parameters

For each parameter the number and percentage of participants in each category and subcategory will be tabulated and listed. All participants in the applicable analysis set will be counted for the denominator of the proportion.

The occurrence (yes/no) as described for the incidence parameters will be analyzed using logistic regression as described above (section 5.3).

Proportions: CRS outcome and CRS (As observed) outcome

A tabulation will be made of the CRS and CRS (As observed) outcomes at each day, taking only non-missing values into account (i.e.: the percentages of the six categories per day should sum up to 100%).

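### Time to mechanical ventilation: censoring deaths and reporting one minus Kaplan-Meier overstates the proportion ventilated, and the log-rank comparison can mislead if early death is informative

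*SAP*

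**What the plan says.** SAP 5.4.1 adds a time-to-event endpoint for mechanical ventilation, modelled on the primary endpoint but with CRS 5 as the event. "This endpoint will be evaluated in the subgroup of participants for which the CRS is less than 5 at Baseline". Its rule for death is: "Participants who did not evolve to score 5 and who die will be censored at the day of death".

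SAP 5.4.2 sets one method for all time-to-event parameters. The comparison is a log-rank test stratified by age and use of invasive ventilation, and "The tests will be performed 1-sided at a 5% significance level". For description, "Cumulative proportion of patients with an event, by treatment, will be provided using the complement of the Kaplan Meier curve", with the median and "the proportion of participants who with an event on day 7, 14, 21 and 28; all per Kaplan Meier method". No competing-risk estimator is named.

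Other places that bear on the point:

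- **Primary endpoint (SAP 5.2.3).** Participants who die by Day 28 are censored at Day 28, so they stay in the risk set as non-improvers.
- **Score 5 (SAP 5.2.1, Attachment 3).** It also covers participants who were not ventilated but medically should have been.
- **Protocol 5.2, exclusion 2.** Patients who meet criteria not to be ventilated, or who have a DNR designation, are excluded.
- **Protocol 9.4.4.** Progression to mechanical ventilation, among those not ventilated at baseline, was planned as a difference in cumulative incidence at Day 28 using the key secondary methods. SAP 5.4.1 lists no such parameter.
- **SAP 5.4.1, ventilation free survival.** It requires CRS 1 to 4 at Day 28, so death counts as failure.

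**The concern.** A participant who dies without reaching score 5 can no longer be ventilated. Censoring at death makes Kaplan-Meier treat that participant as still able to be ventilated later, at the same rate as those who remain at risk. One minus Kaplan-Meier then answers a hypothetical question: what share would be ventilated if nobody died first. Yet the SAP labels it the proportion of patients with an event. That label is wrong whenever ventilations follow unventilated deaths.

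Two things are at stake, and they should be kept apart. One is the reported proportion ventilated in each arm. The other is the between-arm comparison: death is worse than ventilation on this scale, so a test that removes the dead from the risk set could give a favourable impression if the sickest participants die before they are ventilated.

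**Working it through.** **Inputs from the documents.** Planned size of the critical population: "with approximately 74 participants in the Sirukumab treatment arm and approximately 37 participants in the control arm". The number with baseline CRS below 5 is not given. For deaths, "For the mortality rate in the control arm, 40% by Day 28 is assumed", against 20% assumed on sirukumab. These are all deaths, before or after ventilation. The plan states no figure for this endpoint, so there is none to reproduce.

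**Assumptions (not in the documents).** The share ventilated by Day 28 (V), the share dying before ventilation (D), and constant hazards.

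**1. Size of the overstatement.** The true cumulative incidence is V. With ventilation hazard λv and death hazard λd over T days, V = λv/(λv+λd) × [1 − exp(−(λv+λd)T)] and one minus Kaplan-Meier = 1 − exp(−λvT). Eliminating the hazards gives

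1 − KM = 1 − (1 − V − D)^(V/(V+D)).

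For V = 30% and D = 10%: 1 − 0.60^0.75 = 31.8%, an overstatement of 1.8 points.

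| D, with V = 30% | 1 − KM | Overstatement (points) |
|---|---|---|
| 2% | 30.3% | 0.3 |
| 5% | 30.9% | 0.9 |
| 10% | 31.8% | 1.8 |
| 20% | 34.0% | 4.0 |
| 40% | 40.3% | 10.3 |

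A separate simulation of 200,000 participants used a daily ventilation hazard of 0.012 and death hazards of 0.002, 0.004 and 0.008 (about 5%, 9% and 17% dying unventilated). One minus Kaplan-Meier was 27.7%, 27.7% and 27.8%. The cumulative incidence was 27.0%, 26.3% and 25.2%. The gaps are 0.7, 1.4 and 2.6 points.

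**2. Difference between arms.** As an illustration, suppose half of the planned deaths precede ventilation (20% control, 10% sirukumab) and 30% are truly ventilated in each arm. The table gives 34.0% and 31.8%: a gap of 2.2 points where the true gap is zero.

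**3. The log-rank comparison.** Simulated with 74 against 37, unstratified, one-sided 5%, 3,000 runs (Monte Carlo standard error near 5%: √(0.05 × 0.95/3000) = 0.4 points). With identical arms the test was favourable in 5.9% of runs.

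- *Independent hazards, same ventilation hazard (35% by Day 28 if nobody died).* One minus Kaplan-Meier stays at 35.0% whether the death risk in the absence of ventilation is 5%, 20% or 40%. The cumulative incidence of ventilation falls from 34.2% to 31.6% to 27.9%. With death risk doubled on sirukumab (10% to 20%, or 20% to 40%), the test favours sirukumab in 5.8-5.9% of runs, no more than with identical arms.
- *Shared frailty (variance 1 to 2): sicker participants are at higher risk of both events.* With death risk before frailty of 20% against 40%, the test favours the arm with more deaths in 8.8-9.4% of runs. With 10% against 20% it does so in 6.3-7.0%, barely above the reference.
- *Deaths replace ventilations.* Control has 35% ventilated and 5% dead first; sirukumab has 25% and 15%. Ventilation or death is 40% in both. One minus Kaplan-Meier is 36.0% against 27.3%, and the cause-specific hazard ratio is 0.625/0.875 = 0.71. The test is favourable in 25% of runs (20% at 50 against 25; 36% at 140 against 70). For ventilation or death it is favourable in 5.8%.

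**The case against.** Two stronger readings are tempting, and the documents do not support either.

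The first is that the plan automatically rewards an arm whose participants die before ventilation. It does not. With independent hazards, one minus Kaplan-Meier does not move as deaths rise and the log-rank test behaves as it does with identical arms. The two effects even run in opposite directions: measured against the true cumulative incidence, the overstatement is larger in the arm with more deaths and so counts against it. A favourable distortion needs informative death or substitution of death for ventilation. Nor would cumulative incidence alone cure it, since that falls as deaths rise and so looks better in the deadlier arm.

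The second is that this endpoint alone lets death pass as neutral. The SAP also restricts time to discharge (in one version), length of hospitalization and the analysis of ventilation free days to those alive at Day 28, which drops the dead altogether. The contrast with the primary endpoint is not decisive either. Ventilation is an unfavourable event, so holding deaths to Day 28 would record the dead as never ventilated. Censoring at death is the usual cause-specific analysis.

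It is also fair to say that the effect is small. The standard error of a 27% proportion with 37 controls is √(0.27 × 0.73/37) = 7.3 points, and fewer than 37 may qualify. Death is captured by ventilation free survival, Day 28 mortality and the ordinal analyses. The endpoint is absent from the objectives tables and lies outside the testing hierarchy.

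All of this limits the consequence. It does not make one minus Kaplan-Meier a valid estimate of the proportion ventilated, and none of the other endpoints corrects that figure.

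**Conclusion.** The point holds as a minor one. The cumulative and Day 7, 14, 21 and 28 proportions ventilated will be biased upward if ventilations follow unventilated deaths. On assumed rates of about 27-30% ventilated, the bias is roughly 0.7-1 point if 5% die unventilated and 2.6-4 points if 17-20% do. The lower end is more likely, because score 5 includes ventilation that was indicated but not given and because do-not-ventilate and DNR patients are excluded. The bias need not be equal between arms if mortality differs.

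For the comparison, the conclusion is conditional: no distortion if death is independent of ventilation risk, and possible favour to an arm with more early deaths if death is informative or replaces ventilation. The documents do not settle which applies. The simulated error rates depend on the assumed hazards and on an unstratified test.

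This is an other secondary endpoint, so the primary and key secondary conclusions do not depend on it.

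**What to change.** For this endpoint, amend SAP 5.4.1 and 5.4.2 as follows:

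- Replace one minus Kaplan-Meier with the Aalen-Johansen cumulative incidence of ventilation, with death as a competing event, and show it beside the cumulative incidence of death before ventilation. The pair is needed because the first curve alone can look better when deaths rise.
- Add time to ventilation or death (CRS 5 or 6) with the stratified log-rank test, and keep the present cause-specific log-rank test as supportive.
- Restore the Day 28 cumulative incidence of progression to ventilation planned in protocol 9.4.4, or state why it was left out.

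The cost is SAP wording and one more standard analysis. Date of death and daily CRS are already needed to derive the existing endpoints, so no new data are required.

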To evaluate the clinical response of sirukumab + SOC compared to placebo + SOC in confirmed (a) critical and (b) severe or critical COVID-19 disease	
 Time to improvement^a of at least 1 category relative to Baseline on the 6-point ordinal clinical recovery scale (up to Day 28) Proportion of participants with an improvement on Day 28 of at least 1 category relative to Baseline on the 6-point ordinal clinical recovery scale Time from study intervention to end of oxygen supplementation (up to Day 28) Time from study intervention to hospital discharge among the surviving participants (up to Day 28) Total length of hospitalization among the surviving participants (up to Day 28) Number of ventilation free days (up to Day 28) Participant's clinical status at Day 7, 14, 21, 28 (6-point ordinal clinical recovery scale) Total time on invasive mechanical ventilation Proportion of participants with a worse^b category relative to Baseline on the 6-point ordinal clinical recovery scale (up to Day 28) Proportion of participants on extracorporeal membrane oxygenation (ECMO) over time Total time on ECMO
To evaluate the safety during follow-up for (a) critical and (b) severe or critical COVID-19 disease	
 Proportion of alive participants at Day 28, Week 8, and Week 16 Proportion of alive participants that required readmission at Week 8 and Week 16 (if previously discharged) Incidence of SAEs up to Week 16
Exploratory	
To evaluate biomarkers that may be associated with response to or complications of sirukumab treatment	Evaluations may include, but are not limited to, IL-6, procalcitonin, C-Reactive protein (CRP), ferritin, LDH and D-dimer serum concentrations (through Day 28)
To explore changes in SARS-CoV-2 viral load and viral genome	
 Time to SARS-CoV-2 undetectable viral load by RT-PCR (up to Day 28) SARS-CoV-2 viral load over time by RT-PCR (up to Day 28)

^a The improvement should be sustained until Day 28 (or discharge/discontinuation).^b Clinical recovery scale score worsened with at least 1 category between Day 5 and Day 28.

Objectives	Endpoints
	
 Proportion of participants with undetectable viral load (at multiple time points up to Day 28) Development of SARS-CoV-2 variants

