2.2.3 Primary Analysis Set

The Primary analysis set consists of all participants in the ITT analysis set with confirmed critical COVID-19 disease defined as score of 4 or 5 on the CRS scale at baseline. For more details on CRS score please refer to Section 5: Efficacy. Treatment groups as randomized will be used for the analysis using this analysis set (Primary analysis set as Randomized).

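### SAP 5.4.1 narrows ventilation-free days to participants ventilated at baseline, so the Primary and ITT analyses coincide and later ventilated days go uncounted; its handling of discontinuers and deaths also needs repair

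*SAP*

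**What the plan says.** Protocol section 3 lists "Number of ventilation free days (up to Day 28") under an objective that compares sirukumab with placebo, each on top of SOC: "compared to placebo + SOC in confirmed (a) critical and (b) severe or critical COVID-19 disease". The objectives table in SAP 1.1 repeats the endpoint in the same unrestricted form.

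SAP 5.4.1 gives the only working definition: "Number of ventilation free days in participants on IMV/ECMO at baseline (up to Day 28) (days"). The value is the Day 28 date minus the "maximum date of day with score" of 5 or more. It adds: "Participants who die will be considered as being on IMV/ECMO until day 28".

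SAP 5.4.2 then states: "The secondary endpoint evaluation will be conducted on the primary and on the ITT population". Under duration parameters it limits both the descriptive statistics and the Hodges-Lehmann comparison to participants still alive at Day 28.

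The Primary set is the part of the ITT set with "confirmed critical COVID-19 disease defined as score of 4 or 5 on the CRS scale at baseline".

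For total length of hospitalization, the row just above ventilation-free days in SAP 5.4.1, there is an explicit rule: "The total length of hospitalization will be missing for participants who discontinue the trial for other reason than death before day 28". The ventilation row has no counterpart.

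**The concern.** A listed secondary endpoint has been made smaller in the SAP without explanation. Protocol 9.4.4 allows the SAP to add secondary parameters; it does not mention narrowing a listed one. The restriction makes one of the two required analyses a copy of the other. It also removes the participants in whom ventilation after randomisation would be a new event, in a trial whose stated population is at risk of progressing to severe ARDS.

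Two further gaps sit in the same row. A formula that subtracts the last observed ventilated day treats everything after it as free of ventilation, including days nobody observed. And scoring deaths as ventilated to Day 28 has no effect if deaths are excluded from the analysis.

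**Working it through.** The plan states no figure for this endpoint, so there is nothing to reproduce. The check is set membership followed by the SAP formula applied to example histories.

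**1. Who is analysed.** Severe disease is category 3 (Protocol 5.1, note to criterion 5). The Primary set is baseline score 4 or 5 (SAP 2.2.3). IMV or ECMO at any time on the day gives score 5 (SAP 5.2.1). Let E be the participants on IMV/ECMO at baseline; all of E score 5. Then ITT ∩ E = E and Primary ∩ E = E, so the two analyses use identical people.

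**2. How many are left out.** Planned critical participants: about 111. Severe participants already enrolled: about 100 (both SAP 1.4). Total: about 211. The share of critical participants ventilated at baseline is not given; 10% to 50% is assumed.

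| Assumed share | Analysed | Left out of 211 |
|---|---|---|
| 10% | 111 × 0.10 ≈ 11 | 200 (95%) |
| 30% | 111 × 0.30 ≈ 33 | 178 (84%) |
| 50% | 111 × 0.50 ≈ 56 | 155 (74%) |

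These counts are before the restriction to survivors.

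**3. What the formula returns.**

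| Days at score 5 | SAP formula | Days 1–28 with score below 5 |
|---|---|---|
| 1–10 | 28 − 10 = 18 | 28 − 10 = 18 |
| 11–20 | 28 − 20 = 8 | 28 − 10 = 18 |
| none | no last day, so undefined | 28 |

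The second and third histories cannot arise under the present restriction. They show that lifting it without changing the formula would not be enough.

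**4. Discontinuation alive.** The score is missing after discontinuation for a reason other than death (SAP 5.2.1). Take someone at score 5 on Days 1–6 who withdraws on Day 6. The formula returns 28 − 6 = 22, all of it unobserved. Whether that value enters the analysis depends on whether the participant counts as alive at Day 28, which the SAP does not settle for this endpoint.

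**5. Deaths.** Being treated as ventilated to Day 28 gives 28 − 28 = 0. Because SAP 5.4.2 keeps only participants alive at Day 28, no such zero is ever analysed. Protocol section 3 attaches a survivor condition to length of hospitalization but not to ventilation-free days.

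**The case against.** The best defence is that the SAP divides the question on purpose. Time to mechanical ventilation covers participants with a baseline score below 5, in both analysis sets. Ventilation-free days covers those already ventilated. Ventilation-free survival and worsening on the scale (all in SAP 5.4.1) also register later intubation. This largely stands. A reader might infer that the trial cannot show whether the drug prevents ventilation, or that the severe-or-critical objective goes unanswered. The documents do not support either reading: that objective carries eleven endpoints, and only this one collapses. What the pairing does not supply is duration. Total time on IMV and total time on ECMO are listed in SAP 1.1 but have no definition in 5.4.1.

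A reader might also infer that a participant withdrawn while ventilated is certain to be credited with false days. That goes too far. The survivor restriction may remove the participant. The mortality estimand (SAP 5.3.2) counts discontinuers with a score above 1 as dead, though that rule is written for mortality alone. The route is also narrow. Withdrawal is for loss to follow-up, consent withdrawal or death (Protocol 7.2), loss to follow-up concerns the phone visits (7.3), and transfer to another hospital carries the score forward (SAP 5.2.1). The supportable statement is that handling is undefined. Nor would one extreme value move a Hodges-Lehmann estimate much.

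Two small limits apply to the population point. Baseline-ventilated participants who are re-intubated stay in the analysis. A missing baseline score may be taken up to 12 hours after randomisation, so a very early intubation could count as baseline.

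**Conclusion.** The point holds for this endpoint. The protocol and the SAP objectives table describe one population, SAP 5.4.1 another, and the two analyses required by SAP 5.4.2 are the same analysis. That follows from the definitions and needs no assumption. The proportion left out, 74% to 95%, rests on the assumed share ventilated at baseline. All of the roughly 100 severe participants are outside in any case.

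The missing rule for discontinuers is a real gap whose effect depends on how survival is classified, and it is probably confined to few people. The conflict between the death rule and the survivor restriction is plain on the text.

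This is an other-secondary endpoint outside the testing hierarchy, so the primary and key secondary conclusions are untouched. It should be corrected before database lock.

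**What to change.** - Define ventilation-free days for all participants in the Primary and ITT sets as the number of days from Day 1 to Day 28 with a score below 5: 28 if never at score 5, and 0 for deaths by Day 28. If another formula is preferred, it must credit days before intubation.
- Reconcile the death rule with SAP 5.4.2: either analyse everyone with deaths at 0, or keep survivors only and delete the death rule.
- For participants who discontinue alive before Day 28, set the value to missing, as for total length of hospitalization, or treat them as ventilated to Day 28 if the last score was 5. State which.
- Keep the result in participants on IMV/ECMO at baseline as a labelled subgroup.

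The cost is SAP wording and one derived variable from daily scores already collected. A day count also credits days between extubation and re-intubation, which the present formula does not, and it needs a rule for intermittently missing scores. The main drawback is ties: many ITT participants will sit at 28 days, so the Hodges-Lehmann estimate there may be close to 0.
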